### 1.1. Study objectives and endpoints

	Objective	Endpoints
Primary		
	To demonstrate the efficacy of ivosidenib based on PFS status at 6 months per Independent Radiology Center (IRC) assessment	
 
- Progression-free survival (PFS) status (as assessed by the IRC per Response Evaluation Criteria in Solid Tumors [RECIST] v1.1) at 6 months after Day 1 (C1D1).
 

Secondary		
	To evaluate the safety and tolerability of ivosidenib	
 
- AEs, SAEs, AEs leading to discontinuation or death. The severity of AEs will be assessed by the National Cancer Institute Common Terminology Criteria for Adverse Events (NCI CTCAE), v 5.0.
 
- Safety laboratory parameters, vital signs, 12-lead ECGs, evaluation of left ventricular ejection fraction (LVEF), Eastern Cooperative Oncology Group (ECOG) performance status (PS), and concomitant medications.
 

	To evaluate the efficacy of ivosidenib on overall survival (OS), progression free survival (PFS), objective response (OR), duration of response (DoR), and time to response (TTR), with response assessed per Investigator and by the IRC.	
 
- OS, defined as the time from Day 1 (C1D1) to date of death due to any cause.
 
- PFS, defined as the time from C1D1 to the date of first documentation of disease progression as assessed by the Investigator and by the IRC per RECIST v1.1 or death due to any cause, whichever occurs first.
 
- OR, defined as objective response (confirmed CR or confirmed PR), as assessed by the Investigator and by the IRC per RECIST v1.1.
 
- DoR, defined as the time from date of first documented confirmed complete response (CR) or confirmed partial response (PR) to date of first documented disease progression or death due to any cause, as assessed by the Investigator and by the IRC per RECIST v1.1.
 
- TTR, defined as the time from Day 1 (C1D1) to date of first documented confirmed CR or confirmed PR for responders, as assessed by the Investigator and by the IRC per RECIST v1.1.
 
- PFS as determined by the Investigator.
 

	To evaluate health-related quality of life (HRQOL) with ivosidenib	
 
- HRQOL as assessed by validated instruments (EORTC-QLQ-C30, EORTC-QLQ-BIL21).
 

[figure not shown]
Objective	Endpoints
To evaluate the PK of ivosidenib	
 
- Health economic outcomes as assessed by the EQ-5D-5L instrument.
 
- Serial or sparse blood sampling at specified time points for determination of plasma concentration time profiles and PK parameters of ivosidenib.
 

To evaluate the PK/PD relationship of ivosidenib and 2-HG in blood samples	
 
- Blood sampling at specified time points for determination of 2-HG levels to characterize the PD effects of ivosidenib.
 

## 1.2. Study design

This is an open-label, single arm, multicenter study of orally administered ivosidenib in Japanese subjects with previously treated IDH1 gene-mutated cholangiocarcinoma.

### 1.2.1. Study plan

The overall study plan is demonstrated in [Figure \(1.2.1\) 1](#). Subjects will continue to receive study treatment until disease progression unless discontinued due to other reasons. Subjects who discontinued treatment for reasons other than disease progression or withdrawal of consent will be followed in PFS follow-up with the same schedule of assessments as before study treatment discontinuation, until documented disease progression the initiation of new anti-cancer therapy, death, withdrawal of consent, or the end of study/study termination, whichever occurs first. OS follow-up assessments will occur approximately every 12 weeks after EOT unless the participant is in PFS follow-up at that time. OS follow-up will continue until all participants have died, withdrawn consent, or are lost to follow-up, or up to 24 months after the last participant enrolled, whichever comes first. Final analysis for OS will be conducted at the end of the study. For the details on study design and measurements to be collected in each period, refer to the [Section 4.4.1](#) of the clinical study protocol (CSP).

If a participant progresses or does not come back for scans while in PFS follow-up, then the OS follow-up assessments will begin at the next planned OS follow-up time point, following the schedule of every 12 weeks.

**1.2.2. Type of randomization**

Randomization is not applicable in this single arm, open-label study.

**1.3. Determination of sample size**

Approximately 10 Japanese subjects will be enrolled in the study.

The primary endpoint is PFS status (as assessed by IRC per RECIST v1.1) at 6 months after Day 1 (C1D1). Assuming a target 6-month PFS rate of 32% and a dropout rate of 10%, the study needs to enroll 10 subjects to provide approximately 84% power to reject the null hypothesis of PFS rate  $\leq 2.6\%$  using exact binomial test at 1-sided significance level of 0.05.

## 2. STATISTICAL HYPOTHESES AND MULTIPLICITY HANDLING

### 2.1. Statistical hypothesis

The following hypothesis test will be conducted using exact binomial test with 1-sided significance level of 0.05 for the primary endpoint (see [Section 5.3.1](#)):

- $H_0$  (null hypotheses):  $\Phi_1 \leq 2.6\%$
- $H_1$  (alternative hypotheses):  $\Phi_1 > 2.6\%$
- $\Phi_1$  is the 6-month PFS rate

### 2.2. Multiplicity handling

Not applicable.

### 3. ANALYSIS SETS

#### 3.1. Analysis sets

The following analysis sets will be evaluated and used for presentation of the data:

- Intent-to-Treat Analysis Set (ITT): All subjects who were included and treated. The ITT will be used for the primary efficacy analyses and is the default analysis set unless otherwise specified.
- Safety Analysis Set (SAS): All subjects who received at least one dose of study treatment. The SAS will be the primary set for the analysis of safety data, unless otherwise specified.
- Per-Protocol Set (PPS): All subjects in the ITT who do not violate the terms of the protocol in a way that would affect the study outcome significantly. The PPS will be used to perform sensitivity analyses for the primary endpoint. In general, subjects who meet the following criteria will be excluded from this analysis set:
  - Do not have histopathologically diagnosed nonresectable or metastatic cholangiocarcinoma.
  - Do not have documented IDH1 gene-mutated disease based on central laboratory testing.
  - Do not have any measurable lesion at baseline as defined by RECIST v1.1 as determined by IRC or by Investigator.
  - Three or more prior systemic therapy in an advanced setting (nonresectable or metastatic)
  - Have received a prior IDH inhibitor.
- Pharmacokinetic Analysis Set (PAS): All subjects who have at least 1 blood sample post-dose providing evaluable PK data for ivosidenib.
- Pharmacodynamic Analysis Set: All participants who have had at least one blood sample providing evaluable plasma 2-HG data for ivosidenib.

#### 3.2. Treatment groups

All subjects enrolled will be administered the study drug orally at a dose of 500 mg (provided as 250 mg strength tablets).

## 4. GENERAL STATISTICAL CONSIDERATIONS

### 4.1. Descriptive statistics

Summaries will be produced for disposition, demographic and baseline disease characteristics and efficacy variables, as appropriate.

For qualitative data, number of observed values, number, and percentage of subjects per class will be presented. Unless otherwise specified in the TLG, no class "Missing" is considered.

For quantitative data, number of observed values, mean, standard deviation (SD), median, first and third quartiles, minimum and maximum will be presented. The geometric mean will also be provided for log-distributed data (if applicable).

Time-to-event endpoints will be estimated using Kaplan-Meier methods. Point estimates and 95% CIs will be provided where appropriate, and estimates of the median and other quantiles, as well as individual time points (e.g., 3-month, 6month, and 12-month rates) will be produced.

## 5. STATISTICAL ANALYSES

### 5.1. Study Subject

#### 5.1.1. Disposition

The number (%) of subjects included in each of the analysis populations listed in [Section 3.1](#) will be summarized.

The number (%) of subjects in the following categories will be provided for all subjects enrolled:

- Enrolled and treated subjects.
- Enrolled and not treated subjects.
- Subjects still on treatment.
- Subjects who discontinued the treatment and the primary reason for treatment discontinuation.
- Subjects still on PFS follow-up.
- Subjects still on OS follow-up.
- Subjects still on study.
- Subjects who did not complete the study as per protocol and the primary reason for study discontinuation.

#### 5.1.2. Important Protocol deviations (IPD)

IPD will be summarized in the ITT set including the following categories:

- Number and percentage of subjects with at least 1 IPD.
- Subjects by number of IPDs (1, 2,  $\geq 3$ ).
- Number and percentage of subjects within each IPD category.

#### 5.1.3. Demographic data and baseline characteristics

Demographic and other baseline variables will be descriptively summarized on ITT set.

##### 5.1.3.1. Demographics and Physical Measurements

- Gender (Female, Male)
- Race (American Indian or Alaska Native, Asian, Black or African American, Native Hawaiian or Other Pacific Island, White, Unknown, Not Reported)
- Age (years)
- Age group (<45,  $\geq 45$  -<65,  $\geq 65$  years)
- Ethnicity (Hispanic or Latino, non-Hispanic or Latino, Unknown, Not Reported)
- Height (cm)
- Weight (kg)
- Body mass index (BMI, kg/m^2)

If age is not collected in the database, it will be calculated as follows: age = [ICF year – birth year].

### 5.1.3.2. Baseline disease and other characteristics

The following baseline characteristics will be summarized based on ITT set:

- IDH1 allele types per central IDH1 testing.
- ECOG at baseline.
- Cholangiocarcinoma type at diagnosis (Intrahepatic Cholangiocarcinoma, Distal Cholangiocarcinoma, Perihilar Cholangiocarcinoma, Unknown Cholangiocarcinoma).
- T/N/M (Tx, Nx, Mx) or Staging (I to IVc) Cholangiocarcinoma at initial diagnosis.
- Extent of disease at Screening (Local/regional, Metastatic).
- Presence of Liver cirrhosis at Screening.
- Biliary drainage/stent related to Cholangiocarcinoma within the past 3 months.
- Presence of Ascites at Screening.
- Ascites related to Cholangiocarcinoma within the past 3 months.
- Paracentesis within the past 3 months.
- Pleural effusion related to Cholangiocarcinoma within the past 3 months.
- Thoracentesis within the past 3 months.

Data on disease characteristics will be provided in by-subject listing.

### 5.1.3.3. Medical and surgical history

Medical and surgical history includes all the relevant medical and surgical history during the lifetime of the subject. Medical and surgical history will be summarized by System Organ Class (SOC) and Preferred Term (PT) on ITT set.

A listing of medical history will also be provided.

## 5.2. Treatments of subjects

### 5.2.1. Extent of exposure and treatment compliance

Extent of exposure will be summarized on the SAS by the following variables:

- Duration of treatment (in months): (Date of the last dose – Date of the first dose + 1)/30.4375
  - For subjects who are still on treatment at a data cut-off date, the data cut-off date will be the date of the last dose.
  - Duration of treatment will be summarized continuously and categorically (e.g. <1, ≥1, ≥3, ≥6, ≥9, ≥12 months).
- Actual Dose Intensity (mg/day): Actual total dose/duration of treatment (days).
- Relative Dose Intensity (%): Actual dose intensity/planned dose intensity, where the planned total daily dose is the dose assigned at the study entry.
- Dose modification (dose reduction, dose interruption) and the reasons for dose modifications.

### 5.2.2. Prior and Concomitant therapies

#### 5.2.2.1. Prior systemic anticancer therapy

Prior therapies will be summarized on the ITT set. Types of therapies (adjuvant, palliative, etc.) will also be summarized.

Duration of last line of therapy (in months) in advanced setting will be summarized, calculated as (end date of the last line of therapy – start date of the last line of therapy + 1)/(30.4375).

In case there are multiple drugs within 1 line of therapy, the outer window rule will be applied to calculate the duration: the earliest start date of all drugs will be the start date, and the latest end date will be the end date for that line. A data listing will be provided and the line that is contributed to the eligibility will be flagged.

#### **5.2.2.2. Prior Local-Regional Therapy**

Prior local or regional therapies will be summarized on ITT set.

A data listing will be provided for prior local-regional therapy, including the type of prior local regional therapy, anatomical location, start date, end date, therapy setting, best response, and date of progression.

#### **5.2.2.3. Prior Surgery for Cholangiocarcinoma**

Prior surgery for cholangiocarcinoma will be summarized on ITT set.

A data listing will be provided for prior surgery, including procedure, location, date of procedure, whether disease recur or progress after the procedure, and date of recurrence or progression.

#### **5.2.2.4. Prior and concomitant medications/procedures**

Prior and concomitant medications, and concomitant procedures will be summarized on ITT set.

Prior medications are those the subject received prior to first study drug administration. Prior medications can be discontinued before first administration or can be ongoing during treatment period.

Concomitant medications and concomitant procedures are defined as ongoing at the time of first study drug administration or that were initiated after the first dose but prior to the last dose plus 28 days (inclusive). If an end date is missing or the medication/procedure is ongoing, the medication/procedure will be included as concomitant medication/procedure.

A given medication can be classified as a prior medication and/or as a concomitant medication. If it cannot be determined whether a given medication was taken prior or concomitantly, it will be considered as prior and concomitant medication. Concomitant procedures can be classified by the similar rule as concomitant medication.

All medications will be coded using the World Health Organization-Drug Dictionary (WHO-DD) using the latest version and will be tabulated by anatomic therapeutic class (ATC) in 4 levels (pharmacological class, pharmacological sub-class, therapeutic class, Preferred name).

In addition, the following data listings will be provided:

- A listing for prior and concomitant medications, with a flag to indicate prior vs. concomitant.
- A listing of concomitant procedures.

### 5.3. Efficacy analyses

Response to treatment will be assessed by the site Investigators and by the IRC using RECIST v1.1.

#### 5.3.1. Primary efficacy endpoint

The primary analysis will be performed on the ITT set.

The progression-free survival (PFS) by IRC is defined as the time in months from Day 1 (C1D1) to the date of the first documentation of disease progression as determined by the IRC per RECIST v1.1 or death due to any cause, whichever occurs first.

PFS = (Earliest Date of Disease Progression or Death – Day 1 Date + 1) / 30.4375.

The primary endpoint is PFS status at 6 months after Day 1 (C1D1). The 6-month PFS rate defined as the probability of subjects who are alive and progression-free at 6 months after Day 1 (C1D1) will be used to assess the primary endpoint. Kaplan-Meier method will be used to estimate the 6-month PFS rate. Exact binomial test with 1-sided significance level of 0.05 will be used to compare the 6-month PFS rate against 2.6%.

Subjects without documentation of disease progression or death at the time of the analysis of PFS will be censored at the date of the last response assessment prior to the start of alternate therapy. See [Table \(5.3.1\) 1](#) for the details on handling of missing response assessments and censoring.

Number of subjects with events, types of events (progression or death), and number of subjects censored, number of subjects for each reason of censoring, Kaplan-Meier estimates, and 95% CIs according to Brookmeyer and Crowley method for the median, Q1 and Q3 for PFS will be presented. Probabilities of event free at selected time points, such as 3-month, 6-month, 9-month, and 12-month, will be presented. Kaplan-Meier curves of PFS will be provided with the number of subjects at risk over time included.

In addition, the concordance of PFS between investigator and IRC assessment will also be summarized.

**Table (5.3.1) 1 Handling of Missing Response Assessment and Censoring for the Primary Analysis of PFS**

Situation	Date of Censoring
No baseline assessment and no death.	Date of the Cycle 1 Day 1
Alternate anticancer systemic treatment started before documented progression (PD) per RECIST 1.1 or death.	Date of last adequate assessment prior to the start of alternate anticancer treatment 
No adequate post-baseline assessment and no death.	Date of the Cycle 1 Day 1
No documented PD per RECIST 1.1 or death before data cut-off date or before permanently discontinued from the study.	Date of last adequate assessment 

Situation	Date of Censoring
Documented PD per RECIST 1.1 or death following a long gap from the previous adequate assessment (e.g., 2 or more consecutive missed scheduled disease status assessments). The long gap is defined as $\geq 95$ days (ie, 12 weeks + 10 days per the protocol defined visit window). If no adequate assessment prior to minimum of (PD, death), the long gap is calculated from the Cycle 1 Day 1.	Date of last adequate assessment prior to the first occurrence of 2 or more consecutive missing scheduled assessments

 Adequate disease assessment is defined as a response assessment other than “not evaluable.” If there is no adequate response assessment prior to the start of anticancer treatment, it will be censored at the date of Cycle 1 Day 1.

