7.2. Methods and measurement times

The efficacy of ivosidenib will be evaluated by assessing response to treatment according to RECIST v1.1 ([Eisenhauer *et al*, 2009](#)) ([Appendix 3](#)).

Radiographic assessments (CT or MRI) to obtain tumor measurements are to be conducted at Screening (Day -21), every 6 weeks (± 5 days) for the first 8 assessments (i.e., through week 48), and every 8 weeks thereafter (± 5 days) from C1D1, independent of dose-delays and/or dose interruptions, and/or at any time when progression of disease is suspected. CT imaging of the chest, abdomen, and pelvis (Torso) with IV contrast should be performed at baseline and on study. For subjects with allergy to IV iodine contrast, CT of the chest without IV contrast and MRI of the abdomen with IV contrast should be performed at baseline and on study. Brain scans with CT or MRI should be performed at baseline in subjects with known treated brain metastases and on study at the same imaging time points as Torso imaging. Bone scans will be performed at baseline if disease is suspected and on study as appropriate as the same imaging time points as Torso imaging. Any ancillary findings on the radiographic assessments will be communicated to the appropriate physician for notification to the subject.

The same method (CT or MRI) should be used consistently for any given subject. For subjects permitted to continue on ivosidenib beyond documented radiographic progression, a new baseline imaging assessment will not be required, and the imaging assessments will continue on the current schedule. For subjects who discontinue study drug for reasons other than disease progression, a response assessment will be conducted at the EOT Visit. Subjects who have not experience disease progression and are alive by EOT will enter PFS follow-up with the same schedule of assessments as before study treatment discontinuation, until documented disease progression, death, start of subsequent anticancer therapy, withdrawal of consent, loss to follow-up, or until the end of study/study termination.

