### 5.3.1.1. Sensitivity analysis

The primary efficacy endpoint may be analyzed based on the PPS using the same method in the primary analysis.

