#### 5.3.2.2. PFS per investigator

PFS per investigator is defined as the time from C1D1 to the date of first documentation of disease progression as assessed by investigator per RECIST v1.1 or death due to any cause, whichever occurs first.

The same censoring rules as the primary endpoint of PFS will be applied to PFS per Investigator.

The analysis for PFS per investigator will be like PFS by IRC (see [Section 5.3.1](#)).

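### The long-gap censoring row in SAP Table (5.3.1) 1 has no month-6 exception, so it censors known failures at the primary landmark; where a subject returns with IRC progression, the 6-month Kaplan-Meier rate is biased upward

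*SAP*

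**What the plan says.** SAP 5.3.1 makes the primary endpoint the IRC-assessed PFS status at 6 months after C1D1. It defines the 6-month rate as the probability of being alive and progression-free at that time, estimates it by Kaplan-Meier in the ITT set, and tests it against 2.6% with a one-sided exact binomial test.

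The narrative there, like Protocol 10.1.2.3.1, describes censoring only for subjects with no documented progression or death. The protocol leaves the detailed rules to the SAP.

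SAP Table (5.3.1) 1 goes further. Its last row applies to "Documented PD per RECIST 1.1 or death following a long gap from the previous adequate assessment", with a long gap set at 95 days or more, and censors at the last adequate assessment before the missed scans. It adds: "If no adequate assessment prior to minimum of (PD, death), the long gap is calculated from the Cycle 1 Day 1". Nothing in the row limits it to events after month 6.

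Protocol 7.2 schedules scans "every 6 weeks (± 5 days) for the first 8 assessments". SAP 1.2.1 provides for the subject who progresses or "does not come back for scans while in PFS follow-up, then the OS follow-up assessments will begin" at the next 12-weekly time point, so a death after scans stop is still recorded.

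The only sensitivity analysis of the primary endpoint is optional and keeps the rule: "The primary efficacy endpoint may be analyzed based on the PPS using the same method in the primary analysis". For Investigator PFS, "The same censoring rules as the primary endpoint of PFS will be applied to PFS per Investigator".

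**The concern.** A long gap makes the date of progression uncertain, which is the usual reason for censoring after missed scans on a time-to-event curve. The primary endpoint here is a status at a fixed time. A subject with IRC progression or death on or before month 6 is certainly not alive and progression-free at month 6, however long the preceding gap. Censoring that subject at an earlier scan drops a known failure and passes the subject's weight to those still at risk.

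At stake is the primary point estimate, in about 10 subjects with no control arm, where one subject can move it by several points. The counts by censoring reason (SAP 5.3.1), the OS analysis (5.3.2.1) and the death listing (5.4.1) may reveal such a case, but none of them re-estimates the 6-month rate.

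**Working it through.** **Inputs.** From SAP 1.3 and 5.3.1: 10 subjects, 10% dropout, target 32%, null 2.6%, one-sided 0.05, 30.4375 days per month. From SAP Table (5.3.1) 1: gap of 95 days or more. From Protocol 7.2: scans at weeks 6, 12, 18 and 24, which are about days 43, 85, 127 and 169, each ±5 days.

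**1. The plan's own figure.** With 10 × 0.9 = 9 evaluable subjects and success at two or more, power = 1 − 0.68^9 − 9 × 0.32 × 0.68^8 = 1 − 0.0311 − 0.1317 = 0.837. The stated 84% reproduces.

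**2. When the row can act before month 6.** Month 6 is 6 × 30.4375 = day 182.6. The earliest event caught is the day of the last adequate scan plus 95.

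| Last adequate scan | Day (window) | Earliest event caught |
|---|---|---|
| None (gap from C1D1) | 1 | 96 |
| Week 6 | 43 (38–48) | 138 (133–143) |
| Week 12 | 85 (80–90) | 180 (175–185) |
| Week 18 | 122 at the earliest | 217 at the earliest |

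Since 182.6 − 95 = 87.6, a week-12 scan matters only if done by day 87. After an adequate week-18 scan the row cannot act before month 6. One missed scan is not enough: week 6 to week 18 is 127 − 43 = 84 days. Two are: week 6 to week 24 is 169 − 43 = 126 days.

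**3. Subjects who miss scans and return.** Take two subjects scanned at week 6 who miss weeks 12 and 18 and return at week 24. The one without progression has an adequate assessment at week 24 and stays at risk through month 6. The one with IRC progression is censored at week 6. Being censored depends on the outcome, so the Kaplan-Meier rate is biased upward.

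Size, with assumed data: 10 subjects, s event-free at month 6, one returner with progression censored at week 6, and k of the other failures at week 6. The correct rate is s/10. The row gives ((10 − k)/10) × s/(9 − k).

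- s = 3 (correct 30%): k = 0 gives 33.3%, k = 3 gives 35.0%, k = 6 gives 40.0%.
- s = 2 (correct 20%): k = 0 gives 22.2%, k = 7 gives 30.0%.

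In simulation with an assumed 32% 6-month PFS and 5% to 30% of subjects missing two scans at random and returning, the row raised the rate by about 0.4 to 4.4 points on average. Counting the progression as an event nearly removed this. The size depends on which scans are assumed missed.

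**4. Subjects who stop scans for good and die by month 6.** A subject with no adequate scan who dies on day 100 has a gap of 99 days and is censored. The date is presumably C1D1, but that is inferred: the row names C1D1 as the start of the gap, and the rows that name it as a censoring date require no death. On that reading the rate is s/9: 33.3% instead of 30% for s = 3, and 22.2% instead of 20% for s = 2.

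A subject who stops scans and survives is, however, also censored at the last adequate scan. Assume exponential PFS with a 32% 6-month rate, 5%, 10% or 30% of subjects stopping at random after C1D1, week 6 or week 12, and a mean of 60 to 200 days from progression to death. The average 6-month rates were then:

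| Analysis | Average rate |
|---|---|
| Complete scans | about 35% |
| Long-gap row as written | 31.5% to 34.8% |
| Deaths counted as events | 29.8% to 34.6% |

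For this route the row was slightly low on average, and counting the deaths was lower still.

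**5. The exact binomial test.** At 2.6%, P(X ≥ 2) = 0.0265, 0.0216 and 0.0171 for n = 10, 9 and 8, while P(X ≥ 1) = 0.2316, 0.2111 and 0.1900. Two successes are needed in each case. The SAP does not say how a censored subject enters the test, but excluding one or two such subjects, or counting them as non-successes, leaves the decision unchanged.

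**The case against.** The strongest defence is that the row is a prespecified choice, within a task the protocol delegates to the SAP, and that it is coherent for subjects who leave scanning for good: those who die after a long gap and those who survive are both censored at the last scan. Counting only the deaths would be selective the other way. After the same gap, a death on day 180 would be a failure and a death on day 190 would still be censored before month 6. This stands for permanent scan loss, where step 4 bears it out on average. It is not one-sided in a small trial: among simulated trials of 10 that contained a case, the row was 0 to 4 points above that trial's complete-scan rate and counting deaths was 0.3 to 5.5 points below, with counting deaths the closer of the two at 5% to 10% stopping. The defence does not reach the returning subject, where those without progression stay at risk and those with it are removed.

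It is also fair that the case may never arise, and that the counts by censoring reason would make it visible. With no such case there is no bias. If an assumed 5% to 30% of subjects stop scanning, a simulation put at least one case in 6% to 29% of trials. Visibility does not correct the estimate, and changing the rule after a case is seen would look data-driven.

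**Conclusion.** The row conflicts with the plan's own landmark definition, because it censors subjects whose month-6 status is a known failure. For a subject who returns after two or more missed scans with IRC progression by month 6, the bias is upward: 3.3 to 10 points from one such subject in the illustration with 3 of 10 event-free. For a death by month 6 after permanent scan loss, the row raises that trial's estimate relative to counting the death, but the average direction of bias depends on why scans stop.

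A reader might infer three stronger things, none of which the documents support:

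- **That the row always makes the rate too high.** This does not hold for permanent scan-stoppers, whose survivors are censored too.
- **That such cases are likely.** The documents give no missed-scan rate, so every frequency here is an assumption.
- **That the trial could be declared positive wrongly.** Two successes are needed at n = 8, 9 or 10, and no change in the test decision is shown.

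The change should be made because it is cheap, and conservative for a single-arm estimate.

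**What to change.** In SAP 5.3.1 and Table (5.3.1) 1:

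- State that, for the 6-month PFS status and its Kaplan-Meier estimate, IRC progression documented at a scan on or before month 6 is an event on its documented date, whatever the preceding gap.
- State that death on or before month 6 is a failure for the 6-month status used in the exact binomial test.
- For deaths after a long gap without scans, report the Kaplan-Meier 6-month rate both ways, as an event on the death date and as censored under the long-gap row, and name one in advance as primary.
- Keep long-gap censoring for the descriptive PFS curve if wanted, labelled as such. Leave the alternate-therapy row unchanged.

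The cost is a few sentences and a table footnote in the SAP, a reported 6-month rate that may be lower, and a second 6-month figure to explain.
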